Appendix A: MIRODERM IFUs

Appendix B: Sample Case Report Forms

Appendix C: Nutritional Guidelines to Improve Wound Healing

ABBREVIATIONS

AE	Adverse Event
CRF	Case Report Form
DFU	DFU
FDA	Food and Drug Administration
ICF	Informed Consent Form
IRB	Institutional Review Board

1 BACKGROUND

More than 23 million people (7.8%) in the United States are believed to have diabetes. Annually, 1 to 4 percent of people with diabetes develop a foot ulcer and that 10 to 25 percent of diabetic patients will have at least one foot ulcer during their lifetime (1) (2).

Diabetic foot ulcers (DFUs) are a chronic wound which commonly result from peripheral neuropathy and/or peripheral arterial disease associated with diabetes (3). The economic impact of DFUs as a subset of chronic wounds is considerable. An estimated annual \$25 billion is spent on treatment of chronic wounds, and diabetes-related amputations cost approximately three billion dollars per year (2). In addition to treatment-related costs, disability and lost wages related to chronic wounds represents a heavy socioeconomic burden (2).

Standard care for treating DFUs address multiple issues and can vary between care providers. Common standard care considerations include wound debridement, pressure reducing strategies, restoring blood flow, maintaining a moist wound environment, wound infection management, and nutritional support (4). Supplemental treatment for chronic ulcers can include topical antimicrobials, hyperbaric oxygen treatment, cellular therapy, growth factors, and skin substitutes. Accelerated healing of chronic DFUs with skin substitutes can improve patient outcomes and mitigate the economic impact of DFUs.

MIRODERM® is a biologic, porcine liver derived, acellular wound treatment matrix. MIRODERM is FDA 510(k) cleared with an indication for the management of wounds including diabetic ulcers (K140510 and K143426). In addition to being porcine based, MIRODERM has several novel properties including an outer facing epithelial basement membrane with a wound facing open collagen matrix and an intact highly vascularized structure. Both of these are thought to improve the probability of epithelialization and cellular integration. Initial data suggest that MIRODERM can be effective in closing long open DFUs which have been refractory to standard of care and other biological products (5)

This clinical trial will rigorously document the ability of MIRODERM to treat hard-to-heal DFUs and further characterize the safety profile of this device.

2 STUDY DEVICE DESCRIPTION

MIRODERM is a noncrosslinked acellular wound matrix that is derived from porcine liver and is processed and stored in a phosphate buffered aqueous solution. MIRODERM is packaged in an inner sterile pouch and outer non-sterile pouch, in a variety of sizes to be trimmed to meet the individual patient's needs.

This device is available in fenestrated and fenestrated plus versions. Fenestrated plus has larger fenestrations than fenestrated. Although identical in composition, biologics, function, and indications, more fenestrated area allows for greater expansion and may facilitate greater exudate drainage.

MIRODERM® Biologic Wound Matrix is intended for the management of wounds including:

- Partial and full thickness wounds;
- Pressure ulcers;
- Venous ulcers;
- Diabetic ulcers;
- Chronic vascular ulcers;
- Tunneled, undermined wounds;
- Surgical wounds (donor sites/grafts, post-Mohs' surgery, post-laser surgery, podiatric, wound dehiscence);
- Trauma wounds (abrasions, lacerations, second-degree burns, and skin tears);
- Draining wounds.

3 RATIONALE

As a novel, highly vascular porcine derived biologic it is believed that MIRODERM wound biologic may heal wounds more successfully and in a shorter time. The rationale is to objectively demonstrate the clinical effectiveness of MIRODERM by empirically determining the proportion of wounds closed and fully describe the time course to closure.

4 OBJECTIVES OF THE CLINICAL INVESTIGATION

4.1 Primary Objective

The primary objective is to document the effectiveness of MIRODERM Biologic Wound Matrix, to close hard-to-heal DFUs at or within 12 weeks of initial treatment.

4.2 Primary Endpoint

The primary endpoint will be the proportion of subjects who achieve wound closure by or at 12-weeks post treatment with MIRODERM.

4.3 Secondary Objectives

Some secondary objectives include but are not limited to:

- Describe the time course to full wound closure
- Determine the subjects' quality of life score before and after treatment
- Characterize the safety profile of MIRODERM and the procedure
- Explore the histological characteristics of those who successfully heal and those who don't

5 RISK EVALUATION

5.1 Potential Risks to Study Patients

MIRODERM wound matrix is a cleared wound care product and will be used in accordance with approved indications and instructions for use (K140510 and K143426). As an observational, post-market study of a commercialized device for approved indications, the risk to a patient participating in this study is not fundamentally different than the risks this patient would encounter undergoing treatment with a porcine derived biologic wound matrix and not participating in this study. Thus, the only risk unique to this study would be inadvertent disclosure of protected health information.

There are risks, not directly associated with study participation, associated with treatment which may include but are not limited to:

- Sensitivity or allergic reaction to porcine material
- Infection
- Additional tissue damage during sharp debridement
- Cellulitis
- Osteomyelitis

5.2 Methods to Minimize Risks

Investigators will be licensed physicians in good standing. Trial centers and investigators will be selected on the basis of experience with DFU pathology, diagnosis and treatment. Investigators and study personnel will be trained on application of the product and the protocol.

The inclusion/exclusion criteria are consistent with the labeled indications and contraindications of MIRODERM Biologic Wound Matrix and will assure that only subjects who are appropriate for treatment with this product are enrolled.

Regular monitoring of the subjects' condition and tracking of adverse events (AEs) related to the device and trial will allow for the quick identification of potential problems with an individual subject as well as the entire cohort.

Again, MIRODERM Biologic Wound Matrix is a commercially available device being used as indicated. The risk to the patient participating in this study is not fundamentally different than that of a patient undergoing treatment for a DFU using a porcine derived biologic wound matrix and not participating in a study.

5.3 Potential Benefits of the Procedure

The potential benefit of treatment with MIRODERM Biologic Wound Matrix is closure of the refractory DFU and a reduction in the probability of infection, increased wound area and eventually amputation of the affected limb.

6 CLINICAL PROTOCOL

6.1 Study design

This is a multi-center post-market, single-arm, prospective follow-up study evaluating outcomes and efficacy of MIRODERM Biological Wound Matrix to treat hard-to-heal DFUs.

Assessment and Roll-in Phase

Patients who suffer from a persistent neuropathic DFU will be recruited from the investigators practice and network, screened for eligibility, invited to participate in the study and provide informed consent.

The subject's demographics, medical history, co-morbidities and wound characteristics will be documented and the subject will complete a SF-36 quality of life questionnaire. Subject will be instructed on proper nutrition.

The DFU will be treated by the investigator with sharp debridement, be traced, photographed, and dressed per standard of care; dressing will be changed daily by the subject. Two tissue sections of at least 2mm will be retained for histological analysis. Subject will be fitted with and instructed on an offloading device. Subjects will return for MIRODERM treatment in two weeks. At the discretion of the investigator, subjects may also be seen 1-week after initial visit; however, this interim visit is not required by the study and will not be documented.

Treatment Phase

On treatment day, subjects will have their wound debrided as necessary, photographed, assessed using the E-Z Graph Wound Assessment System and treated using MIRODERM. They will be asked to return weekly for dressing and wound assessment. After treatment with MIRODERM, subjects will be considered enrolled into the trial. Details of treatment will be documented.

Weekly, for up to 12 weeks, subjects will return, have their wound assessed for closure. As clinically appropriate, they may have their wound debrided and treated using MIRODERM. The wound will be photographed and assessed using the E-Z Graph Wound Assessment System and treatment details will be documented as applicable. The subject will receive a \$25 gift card for attending the follow-up visit.

If wound has not closed, the dressing will be changed (subsequent to any needed treatment as described in the above paragraph) and the subject will return the following week. If the wound is healed subject will return for a confirmation visit one week later. If, after 12 weeks, the wound is not healed, subject will complete a SF-36 quality of life survey, two tissue sections of at least 2mm from the wound area will be collected and the subject will be discontinued from the study per protocol.

Confirmation Phase

Subject will complete a quality of life assessment and have their wound area photographed. Physician will confirm the wound is still closed and the subject will be discontinued per protocol. If wound has reopened subject will return to the treatment phase.

Subjects whose wound has been assessed closed will return for a confirmation visit. The wound will be assessed for closure. If the wound is still closed, the wound area will be photographed, the subject will complete a SF-36 quality of life survey and be discontinued from the study per protocol. If wound has reopened, subject will return to the follow-up phase at the appropriate post-treatment week continuing there until wound closure or through 12 weeks of follow-up as described in “Treatment Phase” above.

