
Schedule of Visits
	
 1 Assessment and Roll-in (2-weeks prior to procedure) 2 Index Procedure 3 1-Week post-procedure (\pm 2 days) 4 2-Week post-procedure (\pm 2 days) 5 3-Week post-procedure (\pm 2 days) 6 4-Week post-procedure (\pm 2 days) 7 5-Week post-procedure (\pm 2 days) 8 6-Week post-procedure (\pm 2 days) 9 7-Week post-procedure (\pm 2 days) 10 8-Week post-procedure (\pm 2 days) 11 9-Week post-procedure (\pm 2 days) 12 10-Week post-procedure (\pm 2 days) 13 11-Week post-procedure (\pm 2 days)

	
14 12-Week post-procedure (\pm 2 days)
 
15 Confirmation: 13-Week post-procedure (\pm 2 days)
 
All subjects will be offered a \$25 gift card for completing weekly follow-up during the treatment phase.

Study Duration	1 Year
Assessment Tools	
Ankle Brachial Index
 
HbA1c
 
Monofilament test for neuropathy
 
Photograph
 
E-Z Graph Wound Assessment System
 
Sf-36v2 Health Survey

Primary Endpoint	Proportion of subjects who have a closed wound at or before 12 weeks after the index procedure.
Primary Hypothesis	
As an observational study, there is no formal hypothesis test. The precision of the estimate of the proportion of subjects who successfully close will be determined.
 
Assumptions:
 
 • A minimum 50 subjects • A 95% Confidence Interval of the estimate • A 2-sided confidence interval • Using exact Clopper-Pearson estimation 
The Confidence Intervals (CI) at selected success rates are as follows:
 
 • @ 25%; CI = 25.4% Boundaries 13.8%-39.3% • @ 50%; CI = 28.9% Boundaries 35.5%-64.5% • @ 75%; CI = 25.4% Boundaries 60.7%-86.2% 
Thus, a sample size of 50 should allow for a reasonable estimate of treatment success at 12 weeks and for reasonable comparisons to historical controls.

Statistical Analysis	
Descriptive statistics including but not limited to mean, standard deviation, frequency and percentages will be used to describe demographics, medical history, and characterize baseline variable as appropriate.
 
A Z-test will be used to assess whether the proportion of subjects that were successful is greater than zero. Kaplan-Meier analysis will be used describe the survival curve assuming complete closure as the event of interest. A repeated measure ANOVA will be used to assess changes in, wound area and quality of life over time.

TABLE OF CONTENTS

1	Background	13

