6.5.4 Health Survey

Subjects will complete a SF-36v2® Health Survey

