6.7.4 Follow-up Stipend

Subjects will receive a \$25 gift card at each follow-up. Distribution of gift card will be documented.

The following activities will be completed by subjects who present at the 12-week post-treatment visit and have a wound that is not fully closed.

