6.10.5 SF-36v2® Health Survey CRF

The SF-36 is a validated instrument which assesses an individual's current health status and health related quality of life and can be used in health economic analysis. The SF-36 assess 8 sub-scales, vitality, physical functioning, bodily pain, general health perceptions, physical role functioning, emotional role functioning, social role functioning, and mental health. The subscales may also be summarized in two measures assessing physical health and mental health. The SF-36 may be administered as a written survey or verbally.

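### The post-treatment SF-36 is timed by the closure outcome, so the pooled quality-of-life change compares baseline with an event-defined exit visit rather than a common time point

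*Combined protocol and SAP*

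**What the plan says.** Baseline is common to all subjects. Section 6.5.4, at the roll-in visit two weeks before the index procedure, states: "Subjects will complete a SF-36v2® Health Survey".

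After treatment the form appears in two places only, and Table 1 (section 6.3) shows none at the treatment visit or the interim follow-up visits.

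- **Unhealed at Week 12.** Section 6.1, Treatment Phase: "If, after 12 weeks, the wound is not healed, subject will complete a SF-36 quality of life survey". The text under 6.7.4 that introduces the survey in 6.7.5 limits it to "subjects who present at the 12-week post-treatment visit and have a wound that is not fully closed", and the Table 1 footnote does the same.
- **Closed.** Under 6.7.1 a subject found closed returns one week later. Section 6.1, second Confirmation paragraph: "If the wound is still closed, the wound area will be photographed, the subject will complete a SF-36 quality of life survey". The subject then exits (6.1 and 6.9).

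On mode, section 6.10.5 says: "The SF-36 may be administered as a written survey or verbally". No rule keeps the mode the same within a subject.

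On analysis, the synopsis says: "A repeated measure ANOVA will be used to assess changes in, wound area and quality of life over time". Section 7 allows either a repeated-measures ANOVA or a Wilcoxon signed-rank test for each outcome, with particular interest in change from pre-treatment values. It leaves missing values out and mentions no adjustment for assessment time or closure status. The objective in 4.3 asks only for scores before and after treatment.

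**The concern.** The outcome decides when quality of life is measured. A subject who closes early gives an early score and leaves. A subject who never closes gives a score at Week 12. A mean change pooled over both mixes different follow-up lengths, and the mixture depends on how many wounds close and when. A reader told that this is change over time would expect a common time point, and there is none after baseline.

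The second issue is what the subject knows when answering. At Week 12 the form is given because the wound has just been judged open. Closers come to the confirmation visit having known the first closure finding for a week. At baseline there is no such result to react to. At stake is the interpretation of the quality-of-life result, including any use of it in health economic work, which 6.10.5 mentions.

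**Working it through.** **Inputs.** Baseline is 2 weeks before index, follow-up visits fall at Weeks 1-12 and the last confirmation is at Week 13 (synopsis, Schedule of Visits). Confirmation is 1 week after closure (6.7.1). Stated participation is 9 to 15 weeks (synopsis and 6.2). Weeks below count from the index procedure; the 2-day windows are ignored.

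**The plan's own figure.** Longest participation is 2 + 12 + 1 = 15 weeks, which reproduces. The stated minimum of 9 corresponds to closure at Week 9 - 2 - 1 = 6. The schedule itself permits closure at Week 1, giving 2 + 1 + 1 = 4 weeks. The only sample-size figures in the plan are the Clopper-Pearson limits for the primary endpoint. They reproduce, and none is given for the SF-36.

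**Timing.** Closure at Week k gives a form at Week k + 1, which is 2 + k + 1 weeks after baseline.

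- Closers, k = 1 to 12: Weeks 2-13, or 4-15 weeks after baseline.
- Closers, k = 6 to 12 (the 9-week minimum): Weeks 7-13, or 9-15 weeks after baseline.
- Unhealed: Week 12, or 2 + 12 = 14 weeks after baseline.

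**Spread (assumption: closures evenly spread over the possible weeks; p = proportion closed).** Mean form time in closers is (2 + 13)/2 = 7.5 or (7 + 13)/2 = 10, a gap to Week 12 of 4.5 or 2.0 weeks. With m possible closure weeks, the share answering at Week 12 is (1 - p) + p/m. The variance is p(m² - 1)/12 + p(1 - p) × gap².

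| Closure weeks | p | Mean form week, all | SD (weeks) | Share at Week 12 |
|---|---|---|---|---|
| 1-12 | 25% | 10.9 | 2.6 | 77% |
| 1-12 | 50% | 9.75 | 3.3 | 54% |
| 1-12 | 75% | 8.6 | 3.6 | 31% |
| 6-12 | 25% | 11.5 | 1.3 | 79% |
| 6-12 | 50% | 11.0 | 1.7 | 57% |
| 6-12 | 75% | 10.5 | 1.9 | 36% |

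**What the ANOVA can show.** With two scores per subject, a repeated-measures ANOVA is the paired t-test (F = t²; a numerical check gave 0.4444 for both). It tests one before/after difference and cannot describe a course over time.

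**Reaction to the result (illustration only).** The mean shift is p × (closer reaction) + (1 - p) × (non-closer reaction). Assumptions: no true change, SD of change 10 points, n = 50, two-sided paired test at 5%, 20,000 simulated trials. The reactions are invented for illustration.

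| Reaction, closers / non-closers | Mean shift at p = 25 / 50 / 75% | Rejection rate |
|---|---|---|
| 0 / 0 | 0 / 0 / 0 | 5.0 / 4.9 / 4.8% |
| +2 / -2 | -1.0 / 0 / +1.0 | 10.4 / 4.7 / 10.6% |
| +5 / 0 | 1.25 / 2.5 / 3.75 | 13.5 / 38.6 / 71.6% |
| +5 / -5 | -2.5 / 0 / +2.5 | 35.7 / 4.8 / 35.7% |

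Size and sign depend on the closure rate and the assumed reactions. The table shows that the pooled test can be moved, not by how much it will be.

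**Order at the visit.** At Week 12 the closure assessment (6.7.1) precedes the form (6.7.5). For the confirmation visit the sections conflict. The synopsis and the first Confirmation paragraph of 6.1 list the survey before the physician's check. The second paragraph, and 6.8.1 followed by 6.8.3, put it after the wound is found still closed. On the first order a reopened wound can yield two post-treatment forms. On the second, a wound closed at Week 12 and reopened at Week 13 yields none.

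**The case against.** The objective asks only for scores before and after treatment, and the plan provides both. The later score falls at a protocol-defined exit, confirmed closure or 12 weeks unhealed. Section 7 already allows a paired test, and the two-score ANOVA is one. This stands: a before/exit comparison is defined by event, so it is wrong to say that it estimates nothing. What remains is that the plan describes it as change over time and pools the two exit routes.

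A reader might infer more, and the documents do not support it:

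- **That the form always follows the verdict.** This is clear at Week 12 only; for the confirmation visit the sections disagree.
- **That the scores do carry a reaction of known size.** If an assumed 2-5 points moved closers up and non-closers down, their contrast would grow by 4-10 points. The documents contain no such figure and plan no such contrast for the SF-36; 4.3 contrasts healed and unhealed subjects only for histology. In the pooled change, opposite reactions partly cancel. Closure may also truly improve quality of life, and this schedule cannot separate the two.
- **That a shift in closure timing must move the mean.** It does so only if scores change with time since index, which the documents do not address.
- **That the timing gap is 4.5 weeks.** That assumes even closure from Week 1. The sponsor's own participation range points nearer to 2 weeks.

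Subjects also see their own wounds, so no ordering of forms removes all knowledge of healing.

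**Conclusion.** The point holds as a matter of schedule and description. Closure status sets the time of the post-treatment SF-36: Weeks 2-13 for confirmed closers (about 7-13 on the stated minimum participation) against Week 12 for unhealed subjects. The pooled change therefore mixes intervals of 4-15 weeks from baseline. Under even closure the average gap between the groups is 2.0 to 4.5 weeks. The result can carry a reaction to the closure finding; its size is unknown, and the simulated rates rest wholly on assumed inputs. The conflicting order at the confirmation visit must be reconciled. This affects one secondary objective in a study without formal hypotheses. The primary closure proportion and its precision are untouched.

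**What to change.** 1. **Collection (6.1, 6.7.5, 6.8.3, Table 1, and the matching synopsis text).** Every subject attending the Week 12 or confirmation visit completes the SF-36 on arrival, before the wound is examined and whatever the closure result. Use the same mode as the subject's baseline form and record it. This settles the conflicting order and gives a form to a subject closed at Week 12 whose wound has reopened at Week 13. It removes that day's verdict, not knowledge of earlier ones.
2. **Analysis (synopsis and section 7).** Describe the analysis as paired change from baseline to the exit visit, not change over time. Report it separately for closed and not-closed subjects, with weeks since index. State that the last form before exit is the exit score, since some subjects will have two.

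**Cost.** The changes are mostly wording. Subjects first found closed at Week 12 and those with reopened wounds complete a second short form, and the subgroups are smaller than the pooled sample. Subjects who exit early for other reasons still have no post-treatment form; report their number.

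**Optional.** A Week 12 form for early closers would give a common time point. It would require changing 6.9, which ends all obligations at exit, and keeping the baseline mode. Verbal administration, allowed by 6.10.5, would introduce a mode difference tied to closure for anyone whose baseline form was written.

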6.2 Sample Size, Subject Participation, and study Duration

This study will enroll up to 50 and no more than 65 subjects over 6 months. Single centers may continue to enroll until a maximum of 25% (13 subjects) of the planned minimum sample size or until, across all centers, the total sample size is reached. Subject participation will be approximately 9.0 to 15.0 Weeks from time of recruitment to study completion at 1) one-week following assessment of wound closer or 2) following 12 weeks of treatment. In both cases subjects will be discontinued from the study per protocol.

Subjects who do not complete the study per protocol may be exited from the study in the following manner:

- Subject presents with osteomyelitis or an infection of the study of the study DFU
- Subject voluntarily withdraws consent.
- Subject lost-to-follow-up
- Subject death

Subjects have the right to withdraw from the study at any time, for any reason or no reason, without jeopardizing their medical care.

